 - History of or current significant cardiac disease including cardiac failure (NYHA functional class II-IV), myocarditis, cardiomyopathy, angina pectoris or myocardial infarction (within 6 months), unstable angina (within 6 months), stroke (within 6 months), TIA (within 6 months), decompensated heart failure requiring hospitalization (within 6 months) or uncontrolled arterial hypertension
 - History of (within the 6 months) or current cardiac disease such as heart failure NYHA class I, history of myocardial infarction prior to enrollment.
 - Patients receiving treatment with beta-blockers for cardiac disease/comorbidities
 - Any other condition which, in the opinion of the investigator, has a potential for AV conduction suppression and/or other risk factors that may require expanded cardiac monitoring
 - Patients diagnosed with right bundle branch block, either at the Screening visit for entry of the study or during the conduct of the study
- 15. Any of the following pulmonary conditions:
 - History of or active severe respiratory disease, including COPD, or pulmonary fibrosis,
 - Tuberculosis, except for history of successfully treated tuberculosis or a history of prophylactic treatment after positive PPD skin reaction

- Patient with severe asthma or asthma requiring regular treatment with oral steroids
- 16. Patients with any of the following hepatic conditions prior to screening:
 - history of alcohol abuse, chronic liver or biliary disease
 - total or conjugated bilirubin greater than 1.5 times ULN range, unless in the context of Gilbert's syndrome
 - alkaline phosphatase (AP) greater than 1.5 times the ULN range
 - AST (SCOT), ALT (SGPT) or Gamma-glutamyl-transferase (GGT) greater than 3 times the ULN range within the last 6 months
- 17. Any of the following abnormal laboratory values prior to screening:
 - Serum creatinine > 1.7 mg/dL (150 umol/L)
 - White blood cells (WBC) count <3,500/mm3 (<3.5 x 10(9)/L), while on oral DMT's at screening, except fingolimod
 - Lymphocyte count <500/mm3 (<0.5 x 10(9)/L) while on all DMT's at screening except fingolimod
 - Serum potassium > ULN
 - Or other clinically significant laboratory assessment (i.e. hypomagnesemia or hypokalemia)
 - For patients previously exposed to natalizumab, anti-JCV antibody positive and index > 1.5
- 18. Patients with the following neurological/psychiatric disorders prior to screening:

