6.1 Study treatment

6.1.1 Investigational and control drugs

Chemical Name: Siponimod

Other Names: BAF312, Mayzent ®

Classification: Oral sphingosine 1-phosphate receptor modulator

The investigational drug siponimod will be provided as film coated tablets. Please refer to the pharmacy manual provided for specific instructions.

The study medication will be administered orally, once daily, with or without food.

Should titrated patient miss one day of titration or more, the patient will need to restart the titration with Day 1 dosing (0.25mg), including Day 1 cardiac assessments (pre-dose ECG and 6-hour post dose heart rate). It is strongly recommended, during the titration phase, that a member of the study staff contact the patient, once daily via phone, to remind them to take their study medication as required. This is because restarting the titration will require the patient to come in for an unscheduled visit to do a pre-dose ECG assessment and 6 hour post-dose heart rate (holter telemetry monitoring).

Furthermore, if maintenance treatment (2mg) is interrupted for 4 or more consecutive daily doses, treatment must be re-initiated with the 5-day titration, including pre-dose ECG and 6-hour post-dose heart rate (holter telemetry monitoring) at an unscheduled visit. Treatment interruptions for up to 3 missed consecutive daily doses does not require re-titration, and treatment should be continued at the maintenance dose level.

If the patient has missed greater than 30 consecutive days of treatment, using his/her best medical judgement, the PI should consider terminating the patient from the study.

Treatment arm	# of patient's	Type of study drug	Compound	Min. Dose	Max. Dose	Frequency	Formulation	Admin Route	Generic acceptabl e
Arm 1	300 - 400	Investigational	Siponimod	0.25 mg	2 mg	Daily	Tablet	Oral	No

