6.1.3 Treatment arms/group

All patients, except those converting from fingolimod, will be assigned at visit 1 (Day 1) to the following single-treatment arm: Siponimod 0.25mg (initial dose). Following initial dose, the titration schedule will be as follows: Day 2 (0.25mg), Day 3 (0.5mg), Day 4 (0.75mg), Day 5 (1.25mg) and Day 6 and for the rest of the study (2.0mg) as shown in Table 6-3.

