6.5 Dose escalation and dose modification

Siponimod dose adjustments are not permitted. Any dose interruptions due to adverse events should be documented in the eCRF and dose administration record.

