6.7.2 Instruction for prescribing and taking study treatment

During the treatment period, siponimod tablets should be taken once daily, preferably at the same time each day. It is advisable to take the study medication with or without food in the morning, normally before 12 noon.

At the start of the core treatment period, for all patients except those converting from fingolimod, siponimod is initially titrated from 0.25mg/day on day 1 to up to 2mg/day on day 6. For fingolimod patients, the titration regimen will be omitted and started directly on 2 mg maintenance dose. Please refer to the pharmacy manual for specific instructions.

Table 6-3 Dose and treatment schedule

Treatment Schedule for All Pretreatment groups except Fingolimod:

Titration Dose

Day of Treatment Target Dose

0.25 mg					
0.25 mg					
0.5 mg					
0.75 mg					
1.25 mg					
Maintenance Dose					
Target Dose					
2 mg					

Treatment So Fingolimod	
Maintenance	Dose Only
Maintenance Day of Treatment	Dose Only Target Dose

All kits of study treatment assigned by the IRT will be recorded in the IRT system.

The first siponimod dose in the core treatment period should be taken while the patient is at the study site. All dosages prescribed and dispensed to the patient and all dose changes during the study must be recorded on the Dosage Administration Record eCRF.

The investigator should promote compliance by instructing the patient to take the study treatment exactly as prescribed and stating compliance is necessary for the patient's safety and validity of the study. The patient should be instructed to contact the investigator if he/she is unable for any reason to take the study medications.

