- During all other study visits, outside of Day 1 (screening, V2, V3, V4 and V5) a qualified study personnel, as determined by the PI, will assess the patient's heart rate.
- Patients will then follow the normal visit schedule in the treatment period and should complete all of the relevant assessments as indicated in Table 8-1.

Patients should have all visits/assessments as outlined in the Assessment schedule Table 8-1 or as close to the designated day/time as possible with an allowed visit window of ± 3 days for visit 1 (BSL), an allowed visit window of ± 5 days for visits 2, 3, 4, 5 and an allowed ± 7 days for the 30-day telephone follow-up. Missed or rescheduled visits should not lead to automatic

Patients who prematurely discontinue the study for any reason should be scheduled for a visit as soon as possible, at which time all of the assessments listed for the final visit will be performed. At this final visit, all dispensed investigational product should be reconciled, and the adverse event and concomitant medications recorded on the eCRF.

End of Treatment/Study (EOT/S) Visit Schedule

discontinuation.

For patients who complete the core treatment period of the study, the end of treatment/study visit should be conducted. No study drug should be taken on the day of EOT/S.

For patients who discontinue study medication prematurely in the core treatment period, the end of treatment/study visit should be conducted when they stop taking study medication.

A follow-up telephone call, 30 days after the end of treatment/study visit, will be conducted for all patients who randomize.

As per Section 4.6, during a Public Health emergency as declared by Local or Regional authorities i.e. pandemic, epidemic or natural disaster that limits or prevents on-site study visits, alternative methods of providing continuing care may be implemented by the investigator as the situation dictates. If allowable by a local Health Authority and depending on operational capabilities, phone calls, virtual contacts (e.g. tele consult) or visits by site staff/ home nursing staff to the participant's home, can replace on-site study visits, for the duration of the disruption until it is safe for the participant to visit the site again.

Table 8-1 Assessment Schedule

Period	Scree	ening	Treatment			End of Treatment/St udy	Follow-up	Unplanned
Visit	Screening	Baseline ¹	Titration Treatment Period			End of Treatment/St udy	Safety	Unscheduled Visit

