- X = assessment to be recorded in the clinical database or received electronically from a vendor
- S = assessment to be recorded in the source documentation only
- 1. All baseline assessment are to be performed prior to siponimod dosing
- 2. Take another heart rate measure 6 hours post Day 1 dose (a Novartis-supplied portable heart rate monitor patch)
- 3. Patients currently taking or having taken teriflunomide in past 8 months will require a washout per label instructions prior to the baseline.
- 4. Patients may opt in or opt out of completing this questionnaire (optional).
- 5. Only SAEs and SAE related medications are to be collected.
- 6. OCT can be done 5 days prior to treatment or on Day 1 prior to treatment refer to Appendix 8.
- 7. ECG to be performed pre-dose on Day 1 (baseline) however, if the ECG assessment meets criteria in the protocol section 8.4.2., dosing cannot be initiated.
- 8. Neurological Exam refer to the protocol section 8.4 Table 8-2 for more details.

- 10. CD19+ titers only for patients previously exposed to ocrelizumab DMT.
- 11. Fingolimod patients will receive an additional telephone call from site staff at the end of BSL (Day 1) as part of additional safety measures.
- 12. There is no longer an ECG at Day 7 (visit 2). Therefore, visit 2 has been grayed-out and no longer applicable.

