16.3 Appendix 3: Specific Renal Alert Criteria and Actions and Event Follow-up

Guidance on monitoring patients with elevated blood pressure: Patients who have at least two out of the three sitting readings of blood pressure (systolic BP \geq 140 and/or diastolic BP \geq 90 mmHg) should be followed up in one month by an unscheduled visit if the scheduled visit is not due. Should systolic BP \geq 140 and/or diastolic BP \geq 90 mmHg values will be confirmed in two sitting readings out of three in the second visit, the patient should be referred to his primary care physician, an independent internist or to the specialty hypertension clinic for evaluation, diagnosis and treatment of hypertension. A standard referral letter provided by Novartis should explain a reason for referral and the information about the investigational drug (BAF312).

Patients with BP values of >180/110 mmHg on any visit during the study should be immediately referred to evaluation, diagnosis and treatment of hypertension.

The study drug should not be discontinued, unless the physician has a reason to do so.

A newly diagnosed hypertension as well as an aggravation of a preexisting condition must be reported as an AE.

Guidance on monitoring of patients with notable lymphopenia: The absolute total WBC, neutrophil and lymphocyte counts will be measured at each visit by the central laboratory. If

Amended Protocol Version No. 05 (clean)

the circulating lymphocyte level drops to $<0.2 \text{ x} 10^9/\text{L}$ when the patient is receiving the minimum study drug dose allowed in the study protocol, the lymphocyte count should be repeated in one week by the central lab to confirm the reading. If the repeat test confirms the lymphocyte count is below $0.2 \text{x} 10^9/\text{L}$ or 200 cells/mm^3 , the study drug must be interrupted and the lymphocytes count needs to be monitored weekly until the level returns to $0.2 \text{ x} 10^9/\text{L}$, then monthly until the level reaches $0.6 \text{x} 10^9/\text{L}$ values. The patient should be continuously evaluated and monitored for infections.

Re-initiation of the study drug can only be considered once the lymphocyte counts increase above $0.6x10^9/L$.

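### Read literally, the lymphopenia repeat-and-interrupt rule applies only on 0.25 mg, so it misses the Day 28 and Day 84 counts taken on 2 mg

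*Protocol*

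**What the plan says.** The rule is in Protocol Appendix 3 (Section 16.3), under the guidance on notable lymphopenia. If the count drops below 0.2 ×10⁹/L "when the patient is receiving the minimum study drug dose allowed in the study protocol, the lymphocyte count should be repeated in one week". If the repeat is also below 0.2, interruption is mandatory. The count is then followed weekly until it is back at 0.2 and monthly until it reaches 0.6, and restart can be considered only above 0.6. The dose condition sits on the first step, so every later step depends on it.

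On dose, the protocol says:

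- The Section 6.1.1 treatment table lists a minimum of 0.25 mg and a maximum of 2 mg. No section calls 2 mg the minimum.
- Section 6.1.3 starts patients on 0.25 mg on Day 1, followed by "Day 2 (0.25mg), Day 3 (0.5mg), Day 4 (0.75mg), Day 5 (1.25mg) and Day 6 and for the rest of the study (2.0mg").
- Section 6.7.2: "For fingolimod patients, the titration regimen will be omitted and started directly on 2 mg maintenance dose". SAP Section 2.1.1.1 applies this to patients enrolled from Amendment 3.
- Section 6.5: "Siponimod dose adjustments are not permitted".
- Section 6.1.1: after four or more consecutive missed maintenance doses, "treatment must be re-initiated with the 5-day titration".

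On counts, Table 8-1 schedules hematology at screening and Days 1, 28, 84 and 168, and allows it at unscheduled visits. Footnote 1 to that table says "All baseline assessment are to be performed prior to siponimod dosing", and footnote 12 removes the Day 7 visit. For the final visit, Section 8 says "No study drug should be taken on the day of EOT/S".

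**The concern.** A condition tied to the lowest allowed dose makes sense where the dose can be stepped down before drug is stopped. This trial has no step-down. The liver rules in Appendix 2 and the other guidance in Appendix 3 carry no such dose condition.

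Patient safety is at stake. Taken at its word, the protocol sets no required repeat and no required interruption for a patient on 2 mg whose count is below 0.2 ×10⁹/L. Sites that read the phrase differently would act differently on the same count.

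The design makes this matter more. Most patients convert without washout, and overlapping immune effects of the prior therapy are a stated interest of the study (Sections 1.1 and 4.1). Exclusion 17 reads "Lymphocyte count <500/mm3 (<0.5 x 10(9)/L) while on all DMT's at screening except fingolimod", so fingolimod converters have no entry floor on lymphocytes. Those enrolled from Amendment 3 also have no planned day on 0.25 mg.

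**Working it through.** The plan states no figure to reproduce here. The check lays the planned dose against the scheduled counts.

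**Days on 0.25 mg.** Planned dosing runs from Day 1 to Day 167, because no drug is taken on Day 168.

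- Titrated patients: Days 1 and 2, so 2/167 = 1.2%.
- Fingolimod converters enrolled from Amendment 3: 0/167.

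**Planned dose at each scheduled count** (windows of ±5 days from Table 8-1):

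| Count | Window | Planned dose | Literal condition met? |
|---|---|---|---|
| Day 1 | drawn pre-dose | none yet | no |
| Day 28 | 28 ± 5 = Days 23–33 | 2 mg | no |
| Day 84 | 84 ± 5 = Days 79–89 | 2 mg | no |
| Day 168 | 168 ± 5 = Days 163–173 | treatment ends; no drug on the visit day | no |

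Days 28 and 84 are the two counts at which interruption could still change exposure. The literal condition is met at 0 of 2.

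**Exceptions.** The 0.25 mg dose can return through re-titration. A scheduled draw would meet the condition only if it happened to fall on a 0.25 mg day. An unscheduled draw on such a day would also meet it.

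**Wait to the next scheduled count if no repeat is done.**

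- After Day 28: 84 − 28 = 56 days; shortest 79 − 33 = 46, longest 89 − 23 = 66.
- After Day 84: 168 − 84 = 84 days; shortest 163 − 89 = 74, longest 173 − 79 = 94.

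The rule, where it applies, asks for 7 days.

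**Patients affected.** Only those with a count below 0.2 ×10⁹/L, and the documents give no rate. Purely as an assumption, 1% of 300 would be 3 patients and 5% of 400 would be 20. The conclusion does not rest on this range.

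**The case against.** The strongest reply is that no site would read the phrase this way. It is not a defined term and does not refer to the Section 6.1.1 table, whose minimum and maximum may simply describe the dose range of an arm that includes titration. The preceding sentence in Appendix 3 says counts are measured at each visit, and the scheduled on-treatment counts fall on 2 mg. The literal reading is also awkward in itself: a titrated patient on 0.25 mg on Day 1 or 2 would be on 2 mg by the one-week repeat. With dose adjustments barred, 2 mg is the only maintenance dose, so it could be called the lowest one allowed.

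There are also other safeguards. Section 8.4.1 has the central laboratory report notable abnormalities to the site, Table 8-1 allows hematology at unscheduled visits, Section 9.1.1 permits interruption for abnormal laboratory values, and Section 10.1.1 requires adverse events to be followed to resolution. On this view, what remains is a wording point.

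Much of this stands. The 2 mg reading is probably what was meant, the documents show no site acting otherwise, and oversight does not vanish. But the text does not state the 2 mg reading, and the only dose labelled as a minimum contradicts it. The other provisions give notification, the means to retest, discretion and general follow-up. None sets a lymphocyte threshold, a one-week repeat, a compulsory stop or the 0.6 restart level. A mandatory rule should not depend on sites setting aside the protocol's own dose table.

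**Conclusion.** The concern holds and should be fixed. As written, the mandatory lymphopenia rule covers neither the Day 28 nor the Day 84 count for a patient on schedule, and the fallback is a wait of 46 to 66 or 74 to 94 days to the next scheduled count.

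This rests on three assumptions: that the minimum dose is the 0.25 mg in the Section 6.1.1 table, that the patient follows the planned schedule, and that the investigator does not use discretion to retest or interrupt sooner. If sites already apply the rule at 2 mg, the practical effect is nil. How many patients would be affected cannot be estimated from the documents. The primary endpoint and its planned analysis are not in question.

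**What to change.** In Appendix 3, replace the clause that ties the rule to the minimum dose with: *while the patient is receiving study drug (any dose)*. Leave the 0.2 and 0.6 ×10⁹/L thresholds and the repeat, interrupt and restart steps as they are. Coverage of the Day 28 and Day 84 counts then goes from 0 of 2 to 2 of 2, whichever way sites had been reading the phrase.

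The cost is one sentence in an amendment or a clarification letter to sites. No scheduled test is added. There may be a few more confirmatory counts and treatment interruptions.

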16.4 Appendix 4: List of generic names of potent inhibitors/inducers of CYP2C9/CYP3A4

The aim of this document is to provide a specific list of drugs that should not be coadministered with siponimod, and a list of drugs that should only be used with additional vigilance.

Due to the constant information arising on drugs, these lists are by no mean exhaustive and medical judgment should always prevail. These lists are adapted to the patient population and the exclusion criteria of the CBAF312AUS02.

Siponimod is extensively metabolized, mainly via CYP2C9 (79.3%), followed by CYP3A4 (18.5%). CYP2C9 is polymorphic and the genotype influences the fractional contributions of the two oxidative metabolism pathways to overall elimination. Physiologically based PK modeling indicates a differential CYP2C9 genotype-dependent inhibition and induction of CYP3A4 pathways. With decreased CYP2C9 metabolic activity in the respective genotypes, a larger effect of the CYP3A4 perpetrators on siponimod exposure is anticipated.

Because of a significant increase in exposure to siponimod, concomitant use of siponimod and drugs that cause moderate CYP2C9 and moderate or strong CYP3A4 inhibition is not allowed. This concomitant drug regimen can consist of a moderate CYP2C9/CYP3A4 dual inhibitor (e.g., fluconazole) or a moderate CYP2C9 inhibitor in combination with a separate - moderate or strong CYP3A4 inhibitor. Caution should be exercised for concomitant use of siponimod with moderate CYP2C9 inhibitors.

Because of a significant decrease in siponimod exposure, concomitant use of siponimod and drugs that cause moderate CYP2C9 and strong CYP3A4 induction is not allowed for all patients. This concomitant drug regimen can consist of moderate CYP2C9/strong CYP3A4 dual inducer (e.g., rifampin or carbamazepine) or a moderate CYP2C9 inducer in combination with a separate strong CYP3A4 inducer. Caution should be exercised for concomitant use of MAYZENT with moderate CYP2C9 inducers.

Table 16-3 Dual moderate CYP2C9/strong or moderate CYP3A4 inhibitors

Fluconazole	
-------------	--

Moderate CYP2C9 inhibitors Table 16-4

Phenybutazone	Oxandrolone	Milk thistle
Ataciguat	AZD1981	Azapropazone
Tienilic acid	Piperine	Bucolome
Fluconazole	amiodarone	Benzbromarone

Table 16-5 Strong CYP3A4 inhibitors

Viekira Pak	Elvitegravir/ritonavir	Telithromycin
Indinavir/ritonavir	Saquinavir/ritonavir	Grapefruit juice DS

Tipranavir/ritonavir	Lopinavir/ritonavir	Ceritinib
Ritonavir	Itraconazole	Conivaptan
Cobicistat	Voriconazole	Nefazodone
Ketoconazole	Mifepristone	Nelfinavir
Indinavir	Mibefradil	Saquinavir
Troleandomycin	LCL161	Ribociclib
Telaprevir	Clarithromycin	Idelalisib
Danoprevir/ritonavir	Posaconazole	Boceprevir

Table 16-6 Moderate CYP3A4 inhibitors

Erythromycin	GSK2647544	Grapefruit juice
Fluconazole	Aprepitant	Tofisopam
Atazanavir/ritonavir	Casopitant	Cyclosporine
Darunavir	Amprenavir	ACT-178882
Diltiazem	Faldaprevir	Ciprofloxacin
Darunavir/ritonavir	Imatinib	Magnolia vine (Schisandra sphenanthera)
Dronedarone	Verapamil	Isavuconazole
Crizotinib	Ravuconazole	Cimetidine
Atazanavit	Nutepitant	FK1706
Letermovir	Nilotinib	

Table 16-7 Dual moderate CYP2C9/moderate or strong CYP3A4 inducers

Rifampin Enzalutamide

Table 16-8 Moderate CYP2C9 inducers

Rifampin	Enzalutamide
Ritonavir	

Table 16-9 Strong CYP3A4 inducers

Rifampin	Carbamazepine
Mitotane	Enzalutamide
Avasimibe	St John's Wort extract
Rifapentine	Lumacaftor
Apalutamide	Rifabutin
Phenytoin	Phenobarbital

Table 16-10 Moderate CYP3A4 inducers

Ritonavir and St John's Wort	Nafcillin
Semagacestat	Talviraline
Efavirenz	Lopinavir
Tipranavir and ritonavir	Daclatasvir and asunaprevir and beclubuvir
Dabrafenib	Modafinil
Lesinurad	PF-06282999
Bosentan	Etravirine
Genistein	Lersivirine
Thioridazine	Telotristat ethyl

^{*}Source: University of Washington, Drug Interaction Database (www.druginteractioninfo.org).

16.5 Appendix 5: Assessing Immunity to Varicella

(https://www.cdc.gov/chickenpox/hcp/immunity.html)

Evidence of immunity to varicella includes any of the following:

Documentation of age-appropriate varicella vaccination;

- Preschool-age children (i.e., age 12 months through 3 years): 1 dose
- School-age children, adolescents, adults: 2 doses
- Laboratory evidence of immunity or laboratory confirmation of disease
- Birth in the United States before 1980 (Should not be considered evidence of immunity for health care personnel, pregnant women, and immunocompromised persons)
- Diagnosis or verification of a history of varicella or herpes zoster by a health care provider

To verify a history of varicella, health care providers should inquire about:

- an epidemiologic link to another typical varicella case or to a laboratory confirmed case, or
- evidence of laboratory confirmation, if testing was performed at the time of acute disease

Persons who have neither an epidemiologic link nor laboratory confirmation of varicella should not be considered as having a valid history of disease. For these persons, a second dose of vaccine is recommended if they previously received only one dose. If a health care provider verifies the diagnosis based on the above criteria, then vaccination is not needed

16.6 Appendix 6: Teriflunomide Accelerated Elimination Program (for patients treated with teriflunomide at screening or within 8 months prior to screening)

All patients treated with teriflunomide at screening or within 8 months prior to screening should undergo accelerated teriflunomide elimination program. This can be done anytime during the Screening Period if a switch in therapy for the patient is imminent or during the Treatment Period, Visit 1, after all inclusion criterion are met by the patient.

Recommended rapid elimination procedure is the administration of oral cholestyramine 8 g three times per day for 11 days. If patients do not tolerate this regimen, then the dosage may be reduced to 4 g three times per day. Teriflunomide levels are not required for this study however could be completed as part of standard of care.

If tolerability issues persist, cholestyramine administration does not need to occur on consecutive days unless there is an acute need to lower teriflunomide levels.

As an alternative to cholestyramine, oral activated charcoal administered as 50 g twice a day for 11 days may be used.

It needs to be documented in the eCRF which elimination treatment was used.

